### 6.2. Exclusion Criteria

[25] have donated blood of more than 450 mL or have participated in a clinical study that required similar blood volume drawn for the past 3 months ~~within the previous 3 months of study screening~~.

#### 9.4.5.1 Glucose Monitoring

- **Documented Glucose Alert Level (Level 1), Plasma Glucose (PG)  $\leq$ 70mg/dL (3.9 mmol/L) hypoglycemia:**
- **Documented Clinically significant hypoglycemia (Level 2) PG  $<$ 54 mg/dL (3.0 mmol/L):**
  - **Symptomatic hypoglycemia:** an event during which typical symptoms of hypoglycemia are accompanied by PG  $\leq$ 54 mg/dL (3.0 mmol/L)
  - **Asymptomatic hypoglycemia:** an event not accompanied by typical symptoms of hypoglycemia but with PG  $<$ 54 mg/dL (3.0 mmol/L)
  - **Unspecified hypoglycemia:** an event during which PG  $\leq$ 54 mg/dL (3.0 mmol/L) but no information relative to symptoms of hypoglycemia was recorded.
- ~~an event during which plasma glucose is  $<$ 54 mg/dL (3.0 mmol/L), where it is considered sufficiently low to indicate serious, clinically important hypoglycemia.~~
- **Severe hypoglycemia (Level 3):**
  - **Severe hypoglycaemia requiring medical attention:** a severe hypoglycemic event when patients require therapy by HCPs (EMTs, emergency room personnel, etc.).

## Appendix 5 Blood Sampling Summary

Purpose	Blood Volume per Sample (mL)	Number of Blood Samples	Total Volume (mL)
Screening tests a,b	17	1	17
Clinical laboratory tests a,b	11 (fasting)	1	11
	9 (non-fasting)	1	9
Pharmacokinetic samples serum insulin lispro	1	25 samples × 4 periods = 100	100
Blood for glucose	0.2	76 samples × 4 periods = 304	60.8
Blood discard for cannula patency	0.25	76 samples × 4 periods = 304	76
C-peptide samples	2.5	12 samples × 4 periods = 48	120
Immunogenicity	5	<del>34</del>	<del>1520</del>
Pharmacogenetics	10	1	10
Total			418423.8
Total for clinical purposes (rounded up to nearest 10 mL)			420430

2. ABBREVIATIONS

Abbreviations pertain to the Statistical Analysis Plan (SAP) only (not the tables, figures and listings [TFLs]).

AE	Adverse event
ALP	Alkaline phosphatase
ALT	Alanine aminotransferase
AUC	Area under the concentration versus time curve
AUC(0-∞)	Area under the concentration versus time curve from time zero to infinity
AUC(0-t _{last})	Area under the concentration versus time curve from time zero to time t, where t is the last time point with a measurable concentration
C _{max}	Maximum observed drug concentration
CI	Confidence interval
CRF	Case Report Form
CSR	Clinical Study Report
CRU	Clinical Research Unit
CV	Coefficient of variation
Early 50% t _{max}	Time to early half-maximal drug concentration
Early 50% tR _{max}	time to half-maximal glucose infusion rate before tR _{max}
EC	Early Clinical
ECG	Electrocardiogram
e.g.	For example (Latin: exempli gratia)
GD	Glucodynamic
GIR	Glucose infusion rate
G _{tot}	Total amount of glucose infused
G _{tot} (0-30min)	Amount of glucose infused from time zero to 30 minutes
G _{tot} (0-1h)	Amount of glucose infused from time zero to 1 hour
ICH	International Council on Harmonisation
late 50% t _{max}	Time to late half-maximal drug concentration
late 50% tR _{max}	Time to half-maximal GIR after tR _{max}
LSmeans	Least square means
LOESS	Locally weighted scatterplot smoothing

MedDRA	Medical Dictionary for Regulatory Activities
MRE	Magnetic resonance elastography
PD	Pharmacodynamic
PG	Plasma glucose
PK	Pharmacokinetic
R_{\max}	Maximum glucose infusion rate
SAP	Statistical Analysis Plan
SC	Subcutaneous
SD	Standard deviation
TBL	Total bilirubin
TFLs	Tables, Figures, and Listings
t_{\max}	Time of maximum observed drug concentration
tR_{\max}	Time to maximum glucose infusion rate
ULN	Upper limit of normal
VAS	Visual analog scale

3. INTRODUCTION

This SAP has been developed after review of the Clinical Study Protocol (final version dated 21 August 2017) and the version 1 SAP (dated 12 October 2017).

This SAP describes the planned analysis of the safety, tolerability, pharmacokinetic (PK) and pharmacodynamic (PD) data from this study. A detailed description of the planned TFLs to be presented in the clinical study report (CSR) is provided in the accompanying TFL shell document.

The intent of this document is to provide guidance for the statistical and PK analyses of data. In general, the analyses are based on information from the protocol, unless they have been modified by agreement between Eli Lilly and Company and Covance Early Clinical (EC) Biometrics. A limited amount of information concerning this study (e.g., objectives, study design) is given to help the reader's interpretation. This SAP must be signed off prior to first subject administration for this study. When the SAP and TFL shells are agreed upon and finalized, they will serve as the template for this study's CSR.

This SAP supersedes the statistical considerations identified in the protocol; where considerations are substantially different, they will be so identified. If additional analyses are required to supplement the planned analyses described in this SAP, they may be performed and will be identified in the CSR. Any substantial deviations from this SAP will be agreed upon between Eli Lilly and Company and Covance EC Biometrics and identified in the CSR. Any minor deviations from the TFLs may not be documented in the CSR.

This SAP is written with consideration of the recommendations outlined in the International Council on Harmonisation (ICH) E9 Guideline entitled Guidance for Industry: Statistical Principles for Clinical Trials¹ and the ICH E3 Guideline entitled Guidance for Industry: Structure and Content of Clinical Study Reports².

4. STUDY OBJECTIVES

4.1 Primary Objective

- To demonstrate the bioequivalence of PK parameters for the LY900014 U-200 versus LY900014 U-100 formulations after subcutaneous (SC) administration to healthy subjects.

4.2 Secondary Objectives

[figure not shown]
- To compare the glucodynamic (GD) responses to LY900014 U-200 versus LY900014 U-100 formulations after SC administration.
- To assess the safety and tolerability of the LY900014 U-200 and LY900014 U-100 formulations.

4.3 Tertiary/Exploratory Objectives

- To compare other PK and GD parameters for LY900014 U-200 versus LY900014 U-100 after SC administration.
- Explore the formation of anti-drug antibodies to insulin lispro.
- To assess C-peptide levels following administration of LY900014.

5. STUDY DESIGN

This is a Phase 1, single-center, investigator- and subject-blind, 4-sequence, 4-period, randomized, replicated-crossover, 10-hour euglycemic clamp study in healthy subjects to compare the PK and GD of insulin lispro in LY900014 U-200 formulation versus insulin lispro in LY900014 U-100 after SC administration of 15 U insulin lispro dose. The treatments will be replicated such that each formulation is administered twice on different occasions to healthy subjects over 4 study periods. Figure 1 illustrates the study design.

Abbreviation: CRU = clinical research unit

*Single dose of LY900014 U-200 or LY900014 U-100 administered subcutaneously to the abdomen

Figure 1. Illustration of study design

Each subject will be administered LY900014 U-200 formulation (on 2 occasions) and LY900014 U-100 formulation (on 2 occasions). Subjects will be randomly assigned to 1 of the 4 dosing sequences (Table 1).

Table 1. Treatment Sequence Example for I8B-MC-ITRQ

Treatment Sequence	Period 1	Period 2	Period 3	Period 4
1	LY900014 U-200	LY900014 U-100	LY900014 U-200	LY900014 U-100
2	LY900014 U-100	LY900014 U-200	LY900014 U-100	LY900014 U-200
3	LY900014 U-200	LY900014 U-100	LY900014 U-100	LY900014 U-200
4	LY900014 U-100	LY900014 U-200	LY900014 U-200	LY900014 U-100

Note: This is only an example table for illustration purpose; subjects will be assigned a treatment sequence according to the actual treatment randomization schedule provided to the unblinded site pharmacist.

Subjects will be required to attend the clinical research unit (CRU) on at least 6 occasions:

- 1 screening visit (may occur up to 28 days prior to randomization)
- 4 inpatient treatment visits for the clamp procedure (Periods 1 to 4) with a wash-out period of ≥ 3 days between discharge and the next admission to the CRU
- 1 follow-up visit (at least 14 days after the last dose).

Subjects will be admitted to the CRU on the evening before each dosing day and will remain in the CRU for the duration of the clamp period and until discharge by the investigator. Subjects are expected to fast for at least 8 hours before each dose. Following dose administration, each subject will undergo an euglycemic clamp procedure of up to 10 hours. Upon completion of the clamp procedures, the subjects will be provided a meal and observed overnight. Subjects will be discharged from the CRU the next day after medical assessments. Subjects may remain in the CRU if deemed necessary for safety monitoring, as determined by the investigator.

Safety will be assessed throughout the study by monitoring adverse events (AEs), clinical laboratory tests, electrocardiograms (ECGs), vital signs measurement and through medical assessments. Study governance considerations are described in detail in Appendix 3 of the protocol.

6. TREATMENTS

The following is a list of the study treatment abbreviations that will be used in the TFLs.

Study Treatment Name	Treatment order in TFL
15 U LY900014 U-100 SC	1
15 U LY900014 U-200 SC	2

7. SAMPLE SIZE JUSTIFICATION

Up to 60 subjects may be enrolled so that approximately 44 subjects complete the study. Forty-four completing subjects in a replicated design will provide at least 95% power to show the 2-sided 90% confidence intervals (CIs) of the ratios of geometric least-squares means (LSmeans) for area under the concentration versus time curve from time zero to infinity ($AUC[0-\infty]$) and area under the concentration versus time curve from time zero to time t, where t is the last time point with a measurable concentration ($AUC[0-t_{last}]$) between LY900014 U-200 and LY900014 U-100 to be within limits of 0.80 to 1.25. This calculation assumes a log-scale standard deviation for within-subject difference of **CCI** and up to a 5% difference in geometric LSmean ratio. There is also at least 95% power to show the 2-sided 90% CI of the ratio of the geometric means for maximum observed drug concentration (C_{max}) between the 2 formulations also within 0.80 to 1.25. This calculation assumes a log-scale standard deviation (SD) for within-subject difference of **CCI** and a 10% difference in geometric LSmean ratio for C_{max} with LY900014 U-200 compared to LY900014 U-100.

In addition, the study is adequately powered to evaluate the GD parameters. There is at least 85% power to show the 2-sided 90% CI of the ratio of the geometric means between the 2 formulations for total amount of glucose infused (G_{tot}) and maximum glucose infusion rate (R_{max}) are within 0.80 to 1.25. This calculation assumes a log-scale SD for within-subject difference of **CCI** for G_{tot} and **CCI** for R_{max} and up to a 10% difference in the LSmean ratios.

Subjects who are randomized but not administered treatment may be replaced to ensure that approximately 44 subjects complete the study. The replacement subjects will assume the same treatment sequence as the subjects who dropped out and will complete that treatment sequence in its entirety.

8. DEFINITION OF ANALYSIS POPULATIONS

The “Safety” population will consist of all subjects who received at least one dose of study drug, whether or not they completed all protocol requirements.

The “Pharmacokinetic” population will consist of all subjects who received at least one dose of study drug and have evaluable PK data.

The “Pharmacodynamic” population will consist of all subjects who received at least one dose of study drug and have evaluable PD data.

All protocol deviations that occur during the study will be considered for their severity/impact and will be taken into consideration when subjects are assigned to analysis populations.

Primary statistical analyses will be conducted on the set of subjects who complete at least the first period of treatment.

Supportive analyses will be done on the key parameters for the subjects who complete all treatment periods.

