## **7.3. Blinding**

Blinding will be maintained throughout the conduct of the study as described in the separate Blinding Plan.

The study is subject- and investigator-blind with reference to the identity of the study drug administered. The CRU pharmacy staff (involved in preparation of study drug for administration) and dosing nurses will be unblinded to the identity of the study drug administered due to the difference in the appearance of the pens. Appropriate measures at the CRU are to be taken to maintain the blind to subjects and blind the CRU staff.

The Lilly clinical pharmacologist (CP)/Lilly study team will be unblinded.

Emergency codes will be available to the investigator. A code that reveals the treatment group for a specific study subject may be opened during the study only if the subject's well-being requires knowledge of the subject's treatment assignment.

In case of an emergency, the investigator has the sole responsibility for determining if unblinding of a subject's treatment assignment is warranted for medical management of the event. The subject's safety must always be the first consideration in making such a determination. If the investigator decides that unblinding is warranted, it is the responsibility of the investigator to promptly document the decision and rationale and notify Lilly as soon as possible.

Upon completion of the study, all codes must be returned to Lilly or its designee.

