### **9.5. Pharmacokinetics**

At the visits and times specified in the Schedule of Activities (Section 2), venous blood samples of approximately 1 mL each will be collected to determine serum concentrations of insulin lispro. Instructions for the collection and handling of blood samples will be provided by the sponsor. The actual date and time (24-hour clock time) of each sampling will be recorded. Failure to obtain blood samples due to clinical reasons, such as problems with venous access, will not be considered protocol violations. However, the CRU personnel will still be required to notify the sponsor in writing to account for missing samples for data reconciliation purpose.

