### 10.3. Statistical Analyses

Statistical analysis of this study will be the responsibility of Eli Lilly and Company or its designee.

Pharmacokinetic/pharmacodynamic analyses will be conducted on data from all subjects who receive at least 1 dose of the study drug and have evaluable PK.

Primary statistical analyses will be conducted on the set of subjects who complete at least the first period of treatment. Supportive analyses may be done on the key parameters for the subjects who complete all treatment periods. Safety analyses will be conducted for all enrolled

subjects who receive at least 1 dose of the study drug whether or not they completed all protocol requirements.

Any change to the data analysis methods described in the protocol will require an amendment only if it changes a principal feature of the protocol. Any other change to the data analysis methods described in the protocol and the justification for making the change will be described in the study results.

Additional exploratory analyses of the data will be conducted as deemed appropriate. Study results may be pooled with the results of other studies for population PK analysis purposes to avoid issues with post hoc analyses and incomplete disclosures of analyses.

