9.3 Pharmacokinetic Analyses

9.3.1 Pharmacokinetic Parameter Estimation

Subjects who completed at least 1 period and had evaluable insulin lispro concentrations will be included in the PK analysis dataset. PK analyses will be conducted using standard noncompartmental methods of analysis using **CCI** on a computer that meets or exceeds the minimum system requirements for these programs. The version of any software used for the analysis will be documented and the program will meet the Lilly requirements of software validation. It is possible that other validated equivalent PK software programs may be utilized if appropriate, warranted, and approved by global PK management.

Free serum insulin lispro concentrations will be used to calculate several PK parameters, including C_{max} , time of maximum observed drug concentration (t_{max}), time to early half-maximal drug concentration (early 50% t_{max}), time to late half-maximal drug concentration (late 50% t_{max}), and $AUC([0-t_{last}])$, area under the concentration versus time curve from time zero to 10 hours ($AUC[0-10h]$), and $AUC(0-\infty)$. Other parameters may be calculated as deemed appropriate, such as partial AUCs.

Although attempts will be made to adhere to the scheduled collection times, it is recognized that situations arise that may compromise the scheduled times. Parameters will be individually calculated for each subject based on actual collection times and presented by summary statistics.

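### Do the differing descriptions of the primary PK analysis set, and the unwritten exclusion rules, put the bioequivalence conclusion at risk?

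*SAP*

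**What the plan says.** Three passages bear on who enters the primary pharmacokinetic comparison.

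- **SAP 8, Pharmacokinetic population:** "all subjects who received at least one dose of study drug and have evaluable PK data". Protocol 10.3 has nearly the same rule: "all subjects who receive at least 1 dose of the study drug and have evaluable PK".
- **SAP 8, primary analysis:** "Primary statistical analyses will be conducted on the set of subjects who complete at least the first period of treatment". Protocol 10.3 says the same.
- **SAP 9.3.1:** "Subjects who completed at least 1 period and had evaluable insulin lispro concentrations will be included in the PK analysis dataset". Protocol 10.3.2.1 repeats it.

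SAP 8 adds that protocol deviations are weighed by severity and impact and "will be taken into consideration when subjects are assigned to analysis populations". Protocol 9.5 says: "Failure to obtain blood samples due to clinical reasons, such as problems with venous access, will not be considered protocol violations". Protocol 7.3 says: "The Lilly clinical pharmacologist (CP)/Lilly study team will be unblinded", and points to a separate Blinding Plan, which was not among the documents reviewed. SAP section 3 says: "This SAP supersedes the statistical considerations identified in the protocol".

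SAP 9.1 generally limits analyses to the relevant population, lists all databased data and highlights excluded subjects. SAP 9.3.2 repeats the analysis in subjects with evaluable data in every period. SAP 3 requires sign-off before the first dose and requires substantial departures to be agreed and identified in the study report.

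**The concern.** Bioequivalence rests on whether one 90% confidence interval per parameter lies within 0.80 to 1.25, so the set that produces the interval should be fixed in advance. Read literally, the three rules admit different subjects. The SAP's precedence over the protocol does not help, because all three rules are in the SAP.

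Three details also appear to be missing: a definition of evaluable, a list of excluding deviations, and a date for the decision. A profile with samples missed for clinical reasons is not a deviation, so its fate turns on the undefined word alone. With the sponsor team unblinded, a reader might fear that a subject could be kept or dropped according to the result. At stake would be the 5% limit on wrongly declaring bioequivalence.

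**Working it through.** **1. The plan's own figure.** SAP 7 claims at least 95% power with 44 completers. The SDs of the within-subject difference are redacted, so the claim can be neither reproduced nor refuted. It can be solved backwards. With two one-sided 5% tests, SE = SD/√n and 3n − 4 degrees of freedom (or n − 4), power at n = 44 is exactly 95% when the SD is 0.34–0.35 for AUC (5% difference) or 0.23–0.26 for Cmax (10% difference). At those limiting SDs (3n − 4 degrees of freedom), power is about 94% with 42 subjects, 93% with 40 and 92% with 38.

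**2. Where the rules part.**

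| Subject | Dosed + evaluable | First period completed | Any period completed + evaluable |
|---|---|---|---|
| All four periods, evaluable | in | in | in |
| Period 1 complete and evaluable, then leaves | in | in | in |
| Period 1 complete, nothing evaluable | out | in | out |
| Period 1 cut short, later periods complete and evaluable | in | out | in |
| Dosed, no period completed, profile still evaluable | in | out | out |

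Row 3 has no parameter value to analyse, so its membership changes nothing. Only rows 4 and 5 matter.

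**3. Row 5.** A single-period subject brings only between-subject information to the SAP 9.3.2 model. Adding such subjects to 44 completers (assumed within-subject SD 0.20–0.30, between-subject SD 0.25–0.30) lowers the SE of the treatment contrast as follows.

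- 1 subject: about 0.1%
- 4 subjects: 0.3–0.5%
- 16 subjects: 1.1–1.8%

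Sixteen is the ceiling (60 − 44 = 16) and would require every non-completer to be of this type.

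**4. Row 4, precision.** Let σ² be the within-subject variance.

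- Four profiles: variance of the difference = σ²(1/2 + 1/2) = σ².
- Three profiles: σ²(1 + 1/2) = 1.5σ².

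Suppose j of 44 subjects are in row 4. Ignoring period adjustment, the strict reading carries information 44 − j and the inclusive reading (44 − j) + j/1.5. The strict interval is wider by the square root of their ratio.

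- j = 1: √(43.67/43) = 1.008
- j = 2: √(43.33/42) = 1.016
- j = 3: √(43/41) = 1.024

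**5. Row 4, verdict.** 60,000 simulated trials per SD, true ratio 0.80, 44 subjects, assumed SD of the difference 0.20, 0.23 and 0.29:

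| j | Readings disagree | At least one reading passes |
|---|---|---|
| 1 | 1.0–1.1% | 5.3–5.7% |
| 2 | 1.4–1.5% | 5.6–5.8% |
| 3 | 1.8% | 5.8–5.9% |

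The last column needs someone to run both readings and keep the better one. A reading fixed without regard to outcome stays at 5%. As a check, outcome-blind removal of 1 to 6 subjects gave 5.0–5.2%.

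**6. How often row 4 could arise.** Each period has one injection. Protocol 9.6 lets the clamp end before 10 hours once glucose is back at baseline without infusion, so an early end is not by itself an incomplete period. A low predose glucose leads to deferral with procedures repeated. A missed sample is not a violation, and one missed out of 25 leaves 24. A dosed subject with a failed Period 1 who then returns should be uncommon, though neither document defines completing a period.

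**The case for a change.** The stronger half of the concern is discretion, not the period wording. Severity and impact name a basis for exclusion but give no operational test. Evaluable could turn on missed samples or, for AUC to infinity, on extrapolation. Highlighted listings show who was left out, but not when that was decided. The completer analysis uses the same undefined word. If 4 to 6 subjects had deviations and the worst one or two were removed with results known, the 5% error would become about 7–9%. Free choice of the worst 1, 2 or 3 among all 44 would give about 10.7%, 18% and 27% in a paired analysis.

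It stands that these details are unwritten in the two documents. The figures do not describe the plan, however. SAP 8 ties discretion to protocol deviations, so removal at will from all 44 is outside it, and the 7–9% requires result-driven removal, which the plan nowhere calls for. Nothing shows that the unblinded sponsor team assigns populations, and the Blinding Plan may already govern that step.

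**Conclusion.** No change follows. One sentence names the primary set. The other two describe the general population and the parameter dataset, and all three can be met together: dosed, evaluable, first period completed. The phrase about the first period is probably loose drafting for at least one period, since SAP 8 sets it against subjects who complete all periods. Analysts would fit the mixed model to the evaluable profiles available. Choosing another reading alters the interval width by about 0.8% to 2.4% when 1 to 3 subjects are affected, and each reading on its own holds the 5% error rate.

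The undefined term, the unlisted deviations and the undated decision are gaps in documentation. Ordinary noncompartmental practice and a routine population sign-off fill them. The listings, the completer analysis and the reporting of substantial departures leave a trail. No wrong result is shown.

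This rests on assumed numbers of affected subjects, assumed SDs for the simulated error rates, and incompleteness of Period 1 being unrelated to a subject's formulation difference.
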